2.2. Secondary Objectives

- 1. Identify biomarkers in both donor and recipient that may confer a clinical response.
- 2. Establish whether or not ongoing FMT maintenance therapy is required for maintenance of clinical benefit in pediatric UC.

3. STUDY DESIGN

3.1. Study Schema

Description

This is a single-center, phase I/II, randomized, prospective, double-blinded, placebocontrolled study of FMT in the treatment of active pediatric UC. The primary aim is to assess safety and feasibility of a weekly FMT maintenance therapy. A total of 60 patients with active UC (as defined by PUCAI score of > 9) will be enrolled and randomized to first receive FMT or placebo (study treatment).

For therapy/placebo induction, a retention enema will be administered according to the treatment arm to which the patient is assigned. FMT by retention enema will afford us the best delivery method equivalent to that previously described by Moayyeddi and Kunde (see Background) for engraftment of donor stool using FMT materials available to us. Subsequent administrations will occur as oral, frozen encapsulated inocula/placebo for 7 weeks. After the first 8 weeks, subjects will have the option to continue on study treatment or switch to open-label FMT. Subjects will be followed by telephone to assess adverse events for a total of 6 months after their last FMT dose.

Patient metadata and stool samples will be collected at key time points. The patient-reported metadata collection technique will allow for numerous clinical correlations to be parsed out using the random forest machine learning capabilities of synthetic learning in microbial ecology (SLiME) to identify taxonomic features associated with important clinical parameters.(22)

An initial subset of 10 subjects will be enrolled in the study (will be limited to only those patients 12 years of age or older and to those who have mild to moderate ulcerative colitis) and randomized to receive FMT or placebo. We'd expect short term adverse events to occur within 7 days of FMT administration. Individual subject safety data will be reviewed by the PI to assess whether FMT appears to be safe in the subject before continuing the subject towards open-label use of FMT.

3.2. Study Population

The study will enroll 60 eligible patients with active UC (as defined by PUCAI score of >9). Patients from the Gastroenterology clinic at Boston Children's Hospital and outside patients referred or self-referring to the clinic will be considered for participation in the study.

3.2.1. Inclusion Criteria

Male and female children and young adults, aged 5 years to 30 years, who meet the following inclusion criteria, will be enrolled in the study.

An initial subset of 10 subjects will be limited to patients with mild to moderate ulcerative colitis (i.e., PUCAI < 65) and to individuals ≥ 12 years of age. If FMT appears to be safe in this subset of patients after 8 weeks in the study (to be assessed by a Data Safety Monitoring Board), expanded enrollment as is described above will occur.

All patients must satisfy below criteria:

- 1. Have UC (PUCAI >9) and have failed, are intolerant to, or have refused first-line maintenance therapy.
- 2. Have had visual or histologic evidence of inflammation confirmed through colonoscopy ideally within 90 days but no more than 105 days prior to randomization.
- 3. Have negative test results for Hepatitis B (HBV), Hepatitis C (HCV), and Human Immunodeficiency Virus (HIV).
- 4. Have a negative urine hCG test if female of childbearing potential.
- 5. Able to swallow antibiotic, FMT or placebo capsules.
- 6. Able to give informed consent and/or assent as appropriate (patients 12-17 will be asked to provide written assent, patients 5-11 will be observed for assent or dissent behaviorally, or with verbal/written communication)
- 7. Willing and able to participate in the study requirements, including serial stool collection, survey completion and clinic visits.
- 8. Willing to undergo telephone follow-up to assess for safety and adverse events.
- 9. Must be free of any known food allergy.
- 10. Agrees and willing to have an enema for purposes of induction therapy.

Patients who have disease that has required other medications (including steroids, immunosuppressives, and biologics) will be included.

3.2.2. Exclusion Criteria

Subjects who fall into any of the following exclusion criteria at the time of screening are not eligible for enrollment into the study.

- 1. Patients in a clinical remission (PUCAI \leq 9).
- 2. Patients with recent (within 4 weeks) dose change of biologics, 5-ASA, steroids or immunomodulators
- 3. Patients considered to have toxic megacolon.
- 4. Patients with a known drug allergy to vancomycin, metronidazole or polymyxin.
- 5. Patients with a history of aspiration, gastroparesis, surgery involving the upper gastrointestinal tract (that might affect upper gastrointestinal motility) or unable to swallow pills.
- 6. Patients with esophageal dysmotility or swallowing dysfunction.
- 7. Patients with known food allergies.
- 8. Patients with positive test results for HBV, HCV, or HIV.
- 9. Female patients with a positive test result on a urine hCG test.
- 10. Patients unwilling or unable to give consent or participate in all study requirements.
- 11. Patients unable or unwilling to receive a retention enema for purposes of induction therapy.

- 12. Patients with recent (within 6 weeks) systemic antibiotic use.
- 13. Patients who have testing consistent with active clostridium difficile.
- 14. Patients with known prior experience with donor FMT.

Research personnel and care providers will be educated about inclusion/exclusion criteria so that only appropriate patients are approached for informed consent. This will reduce the burden of worry for families and patients as to whether they are suitable candidates for the study. Subjects who are found to have no evidence of active disease by colonoscopy will be excluded from the study.

3.2.3. Subject withdrawal criteria

All subjects are free to withdraw from participation in the study at any time, for any reason, specified or unspecified. A subject may be withdrawn from the study under any of the following circumstances:

- Withdrawal of informed consent or assent when applicable.
- If, in the opinion of the investigator, IRB or DSMB, it is no longer in the subject's best interest to continue in the study.
- The subject no longer meets the inclusion criteria or meets any of the exclusion criteria.
- Lack of compliance with study procedures or study treatment, as determined by the investigator.

3.2.4 Screen failure

A subject who consented to participate in the study but who was disqualified during screening procedures and *never began Antibiotic/Placebo conditioning* will enter Passive follow-up, which means the subject may reach out to the study team for a second opinion for follow-up care or any other medically related reason. These subjects will not be included in the per protocol analysis.

4. STUDY TREATMENT

4.1. Investigational Agent

4.1.1. Fecal Microbiota Transplant (FMT) and placebo

The investigational agent consists of screened-donor inoculum of a biologically active human substance (FMT). FMT will be administered using either frozen screened-donor liquid stool (the investigational agent) in the form of retention enema (60 mL total for ages 5-10 and up to 120 mL total for ages greater than 10) or frozen capsules. Placebo will be administered using either placebo liquid or placebo capsules (both consisting of cocoa butter, glycerol, and brown food coloring). Donor material and placebo material will be obtained from Microbiome Health Research Institute (OpenBiome), a stool bank affiliated with the MIT-Broad Institute. All donors will be thoroughly screened for health and infectious status. (Cross ref. **BB-MF 15543**).

If randomized to FMT Arm, subjects will be matched with a specific stool donor and will then receive FMT induction enemas and FMT capsules containing this stool for the 8 week randomized portion of the trial. From each donor, sufficient stool to complete the study will be secured by OpenBiome and stored at their facility under appropriate storage conditions. The 8 week supply of the donor's inoculum will be maintained on-site at BCH and stored in accordance with supplier specifications and investigational agent guidelines. If subjects are eligible for open-label FMT and have previously been randomized to FMT, every effort will be made to use the same donor if possible. It is conceivable that enough stool to continue through open-label FMT treatment period(donors move or may become ineligible for stool donation) will not be practicably available and another appropriate donor may be selected for open-label FMT use if necessary.

4.1.2. Storage and Accountability

The Boston Children's Hospital (BCH) research pharmacy will be responsible for the receipt and accountability of study agent. The pharmacy will maintain accountability logs with quantities received and dispensed, specifying the corresponding dates, and the identification code of the study subject.

Bottles (containing the FMT and placebo enema preparations) and FMT and placebo capsules will be delivered in temperature controlled packaging on dry ice with a time-temperature indicator. The bottles and capsules will be stored at -80°C in an access controlled freezer in accordance with the manufacturer's and BCH Infection Control specifications until dispensed for administration in a clinical research unit (CTSU).

In order to maintain the integrity of the FMT inoculum during storage, the study team will use temperature-controlled, limited access freezers. Each freezer is equipped with a temperature monitoring system that alerts members of the lab and study team if the freezer fails (e.g. power failure or abnormal temperature fluctuations). In the event that a failure does occur and the study drug becomes unusable, the affected items will be voided and discarded.

4.1.3. Administration and Dispensing

The first FMT or placebo dose will be administered as an enema 48 hours after completing antibiotic therapy (Week 1, Day 1). An un-blinded, independent pharmacy technologist will prepare the retention enemas or placebo which will be provided by OpenBiome. An unblinded research study nurse will then dispense FMT or placebo (study treatment) retention enema according to the treatment arm to which the patient is assigned. The enema containers will be fully color-tinted from the tip to the bottom of the container. The container will be placed inside a paper bag, to prevent any odor detection. Both the patient and the study nurse will be required to wear a tightly fitted mask at all times during the infusion and retention of the enema.

Subjects will be put in left lateral decubitus position with elevated hips in a designated private study visit exam room for 60 minutes for FMT induction (or placebo) by retention enema. Each subject will receive FMT (or placebo) as either one or two retention enema(s) over 15-30 minutes. Each 60 mL enema will be infused over 5 minutes. Subjects will be asked to rotate 180° (from left lateral to right lateral position and then return to left lateral position) slowly over a 10 minute period. While 120 mL of fecal solution (or placebo) will be prepared for induction retention enema for patients over the age of 10, the final administered dose will be dependent on subject's comfort and willingness to proceed with the next enema which will be assessed after the first 60 mL enema infusion. Subjects will be monitored by a blinded study nurse for 60 minutes after enema administration for any immediate adverse events and discharged.

For the next 7 weeks of study treatment, an unblinded research pharmacist will dispense FMT (study treatment) or placebo capsules to be administered under observation in the CTSU. 15 capsules of study treatment (the equivalent of 7.5 grams of human stool) will be administered within 90 minutes of thawing once weekly for a total of 7 weeks. After the initial 8 weeks, participants who responded to FMT during the blinded portion of the study or participants who did not respond to placebo will have the option to continue treatment with weekly open-label FMT.

4.1.4. Blinding and Randomization

The first ten eligible subjects will be randomized in a 1:1 ratio according to a pre-determined block randomization procedure to receive either FMT or placebo. If safety allows, the remaining cohort of 50 eligible subjects will be randomized in a 1:1 ratio according to a pre-determined block randomization procedure to receive either FMT or placebo. An unblinded pharmacist or delegate will maintain the randomization list ensuring subjects are randomized appropriately and dispensed the correct treatment. The investigator, research personnel and study subjects will be blinded to treatment assignments.

4.1.5. Drug Related Risks

Theoretically, there is a small potential of transmission of an unknown pathogen when delivering human donor fecal material to a recipient. Additionally, there is potential concern that the recipient might have an allergic reaction to a food component in donor stool that they might not be aware of and the donor has not avoided. There is also a potential that certain disease states might be inherently related to the gut microbial environment and a donor's risk for disease might be transmitted to a recipient. These risks will be mitigated by carefully screening donors for health status as well as relevant (known) infectious pathogens.

The literature to date comprises 100's of cases of FMT for CDI as well as for IBD. To date, no serious adverse events have been reported. Both Vermeire and Vandenplas reported systemic symptoms of fevers and abdominal pain in refractory IBD patients after FMT that resolved within 24-48 hours without intervention. (10,14) Pierog at Columbia University reported the development of granulomatous appendicitis two weeks after FMT for the indication of recurrent CDI in a pediatric patient with underlying ileocecal granulomatous Crohn's disease, but there is no clear reason to assume FMT is responsible for this otherwise Crohn's related outcome. (23) Quera reported a repeated sepsis episode with multi-drug resistant E. coli in a 61 year old male ill Crohn's patient treated by FMT for recurrent CDI who had had several episodes of similar bacteremia previous to FMT. (24) [name] reported a case of a 37 year old man who self-administered FMT at home for his ulcerative colitis who subsequently developed CMV colitis. (25) Additionally, De Leon reported a case of a patient who experienced a transient flare of ulcerative colitis that had been quiescent for twenty years after FMT for recurrent CDI. (26)

Retention enema is likely low-risk but may be less effective in some patients with inability to retain the FMT inoculum or placebo rectally. Mild discomfort and distress with anal manipulation are possible, though enemas are routinely used in our clinical practice to treat distal IBD colitis as well as constipation. Indeed in adult populations with advanced age, multiple comorbidities or limited life expectancy, this delivery mode is preferable. (27)

5. STUDY SCHEDULE AND PROCEDURES

Potential subjects will be assigned a unique identifier or study ID which will be used to identify the subject throughout the study period. Subjects who meet eligibility criteria will be consented and randomized to the FMT or placebo arm.

During the study period, no changes to the previous medical therapy of patients will be made unless clinically indicated. At all times during the study, progression of standard medical therapy will be advised and available if necessary regardless of study drug assignment. Weaning of steroids will be allowed of a patient by PI discretion

5.1. Schedule of Events

SCREENING		BLINDED TREATMENT							OPEN-LABEL FMT						FO	OLLOW	Early Termination		
	Day	Day			Visit Week (± 2 days)			1	Day			Visit Week (± 2 days)			Month				
Procedures	-90 to -9	-8	-1	0 (Wk 1, D1)	2-3	4	5-7	8		-8	-1	0 (Wk 9, D1)	Weekly	Every 4 weeks	1,	2,4,5	3	EOS 6	
Informed Consent	х																		
Eligibility	х								Ş										
MD visit	х			х		х		х	Į DIL			x		х			х	х	
HBV, HCV, HIV ³	х								UNBLINDING										
Lavage	х								NN										
Colonoscopy (up to 105 days)	х																		
Randomization		x																	
Antibiotics ¹ /placebo		Х								\mathbf{X}^{11}									
hCG ³	х	X ⁸				x		x		X^8				х					
Labs ²	х			х		х		х	1			х		х			х	х	х
Disease activity surveys 5	х	х	х	х	х	х	х	х		х	х	х	x			x	х	х	х
Stool sample ^{7,9}		х		х	х	х	х	х		х		х	x				х	х	х
AE assessment by RN/MD		х	х	х	х	х	х	х		х	х	х	х	х		x ⁶	х	х	х
Telephone contact by RN/MD			x								x					х			
FMT/placebo dosing				X^4	х	х	х	х				X ^{4,10}	X ¹⁰						

¹7-day induction regimen of 3 antibiotics (vancomycin 125 mg, polymixin 62.5 mg, and metronidazole) BSA for vancomycin 125 mg, polymixin 62.5 mg = SQRT [(cm*kg)/3600]

<0.5 m²: PO 1 capsule, TID

 $0.5 - 1 \text{ m}^2$: PO 2 capsules, TID

1-1.5 m²: PO 3 capsules, TID

1.5 -2 m²: PO 4 capsules, TID

Metronidazole weight-based dosing parameters

12.5 kg \geq Patient Weight > 25.0 kg: 125 mg PO BID 25.0 kg \geq Patient Weight > 37.5 kg: 250 mg PO BID 37.5 kg \geq Patient Weight > 50.0 kg: 375 mg PO BID Patient Weight \geq 50 kg: 500 mg PO BID

² "Screening labs" are considered for research purposes only, and will be covered by the study. Routine laboratory assessments are per routine clinical care, and if you are a patient at BCH, these will be

covered by the subject's insurance company. If the patient is not seen at BCH, then these are considered for research purposes and will be covered by the study.

³ HBV, HCV, HIV, and hCG testing are research-only labs and are required to be obtained no earlier than 2 weeks prior to the 1st FMT dose.

⁴ Initial FMT/placebo dose (Week 1 of blinded therapy will be administered as a retention enema). Week 1 of open label therapy will be a selective FMT induction enema or FMT weekly capsule.

⁵ Disease activity surveys include the Patient Reported Outcomes Diary and Pediatric Ulcerative Colitis Activity Index

⁶ Weekly telephone AE Assessments will also be conducted on a weekly basis for the 1st month of follow-up.

⁷ IBD Biomarkers (quantitative fecal calprotectin) will be done after study completion from frozen samples taken from every study stool sample.

⁸ A urine pregnancy test should only be obtained on day -8 if one has not been done in the past 30 days.

⁹ The "X" location of stool samples indicates when the stool will be collected from the participant. I.e. stool will be collected from the subject on day -8 and Week 1, Day1 however collection kits will

have been provided to the subject beforehand. Lack of stool sample collection will not constitute a protocol deviation.

¹⁰Subjects in the OL treatment will receive FMT (not placebo)

¹¹ If eligible, subjects in OL treatment will receive selective Antibiotics (no placebo).

¹² If a subject received at least 1 dose of FMP IP.

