0.5-1	2	3 times a day				
1-1.5	3	3 times a day				
1.5-2	4	3 times a day				

*BSA will be calculated as **BSA = SQRT [(cm*kg)/3600]**

2) A third antibiotic metronidazole administered orally (PO) as a separate capsule according to the following weight-based dosing parameters:

Patient Wt (kg)	Dose (mg)	Frequency			
12.5 - 25.0	125	2 times a day			
25.0 - 37.5	250	2 times a day			
37.5 - 50.0	375	2 times a day			
>50.0	500	2 times a day			

Corresponding placebo for each antibiotic will be supplied and distributed by the BCH Research Pharmacy.

Clinical data including symptom logs, medications and disease activity and stool samples will be collected at the time of study entry and after completion of the antibiotic regimen. Routine laboratory analysis will be done at the time of enrollment and before commencing study treatment.

Subjects who meet all eligibility criteria will be randomized to receive either FMT or placebo.

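### Antibiotic dosing bands: three metronidazole inequalities in the schedule footnote are reversed, the two versions conflict at exactly 50.0 kg, some endpoints fall in two rows, and no capsule row exists above 2 m²

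*Combined protocol and SAP*

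**What the plan says.** The seven-day conditioning regimen is specified in two places.

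**Metronidazole, by weight.** Footnote 1 to the schedule in section 5.1 has four lines. The first three place 12.5, 25.0 and 37.5 kg respectively on the left of a greater-than-or-equal sign and continue "Patient Weight > 25.0 kg: 125 mg PO BID", "Patient Weight > 37.5 kg: 250 mg PO BID" and "Patient Weight > 50.0 kg: 375 mg PO BID". The fourth, also introduced by a greater-than-or-equal sign, reads "50 kg: 500 mg PO BID". The table in section 5.2.1 uses the same cut-points as ranges. Its last two rows are "37.5 - 50.0 375 2 times a day" and ">50.0 500 2 times a day".

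**Vancomycin/polymyxin capsules, by body surface area.** Both places give four rows. The last row in the footnote is "1.5 -2 m²: PO 4 capsules, TID", and the last row in 5.2.1 has the same upper limit. BSA is the square root of height (cm) times weight (kg) divided by 3600.

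**Who may be dosed.** Section 3.2.1 admits subjects "aged 5 years to 30 years". Neither 3.2.1 nor 3.2.2 sets a limit on weight or BSA.

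**The concern.** A dosing rule should give each eligible subject exactly one row, and the same row wherever it is printed. Here one printed version is logically empty for its three lower bands, the two versions disagree at one weight, some boundary values have two rows, and large adults have none. Staff working from the schedule, from 5.2.1 or from both could resolve these cases differently.

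The matter falls within what the trial measures. Safety and tolerability are the primary aim (section 2.1). Section 7.3 puts into the primary analysis every eligible randomized subject who took at least one dose of study medication, and counts the antibiotic or placebo week for this purpose. Inconsistent dosing in that week would therefore occur in the primary safety population.

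**Working it through.** The plan gives no derived figure to reproduce. The check applies each rule literally. W is weight in kg.

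**1. Can the footnote bands be met?** They read 12.5 ≥ W > 25.0, then 25.0 ≥ W > 37.5, then 37.5 ≥ W > 50.0. Each needs W at or below the smaller number and above the larger, which is impossible. On a 0.1 kg grid from 10 to 120 kg, no weight satisfies any of the three. Only the fourth line, W ≥ 50, can be met.

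**2. Do the two versions agree?** The last two columns turn the footnote's signs around in the two possible ways. Entries are mg per dose, twice daily.

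| W (kg) | Footnote, literal | 5.2.1 table | Footnote turned: lower limit included | Footnote turned: upper limit included |
|---|---|---|---|---|
| 20 | none | 125 | 125 | 125 |
| 25.0 | none | 125 and 250 | 250 | 125 |
| 30 | none | 250 | 250 | 250 |
| 37.5 | none | 250 and 375 | 375 | 250 |
| 45 | none | 375 | 375 | 375 |
| 50.0 | 500 | 375 | 500 | 375 and 500 |
| 50.1 | 500 | 500 | 500 | 500 |

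At 50.0 kg the difference is 500 − 375 = 125 mg per dose, and 125/375 = 33%. Neither way of turning the signs makes the footnote agree with 5.2.1 there: one gives 500 mg, the other gives both doses.

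**3. Shared endpoints.** In 5.2.1, 25.0 kg and 37.5 kg each fall in two rows, as the table shows. In both capsule tables, 1 m² falls in the rows for 2 and 3 capsules, and 1.5 m² in those for 3 and 4. No tie or rounding rule is stated.

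**4. BSA above 2 m².** Setting √(h × W / 3600) = 2 gives W = 4 × 3600 / h = 14,400 / h, with h the height in cm. The documents give no body sizes, so the heights and weights below are assumptions.

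| Assumed height (cm) | Weight at which BSA = 2 m² (kg) |
|---|---|
| 160 | 90.0 |
| 170 | 84.7 |
| 175 | 82.3 |
| 180 | 80.0 |
| 190 | 75.8 |

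Three assumed adults above the limit:
- 180 cm, 85 kg: √(15,300/3600) = √4.250 = 2.06 m²
- 175 cm, 83 kg: √(14,525/3600) = √4.035 = 2.01 m²
- 185 cm, 80 kg: √(14,800/3600) = √4.111 = 2.03 m²

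None has a row in either capsule table.

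**5. Who is exposed?** In the blinded phase the FMT arm takes the active antibiotics and the placebo arm takes matching placebo for each (section 5.2.1). Under section 5.2.3, subjects randomized to placebo who go on to open-label FMT first take the seven-day antibiotic course.

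**The case against.** **The 5.2.1 table is usable.** This stands. A reader might infer from the footnote that the antibiotic rules as a whole cannot be applied, or that subjects between 12.5 and 50 kg have no dose. The documents do not support that. Section 5.2.1 gives readable metronidazole ranges from 12.5 kg upward, unambiguous away from the shared endpoints, and the capsule tables work up to 2 m² apart from theirs. The footnote repeats the same cut-points and doses, so its intent can largely be guessed.

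**The conflict between versions is a single value.** This also stands. With the reversed signs set aside, 5.2.1 gives a different dose from the footnote only at a recorded weight of exactly 50.0 kg, so few subjects can be affected. The shared endpoints are likewise single values and partly a matter of drafting style.

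**The signs may be a PDF-reading fault.** This cannot be fully excluded from extracted text, but it is unlikely: three consecutive lines are reversed in the same way while the fourth reads correctly. The 50.0 kg conflict and the missing row above 2 m² do not depend on it.

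**The harm is confined to one arm.** A reader might infer that dosing errors could arise only in the FMT arm. Section 5.2.3 contradicts this, because placebo subjects entering open-label FMT also take the antibiotics.

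**The gap above 2 m² rests on assumed body sizes.** True, and no frequency can be given. The gap itself does not rest on them: both tables stop at 2 m² and eligibility sets no upper limit.

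**Conclusion.** The point holds in limited form. Three of the four metronidazole lines in the schedule footnote cannot be met by any weight, while 5.2.1 supplies usable ranges for the same cut-points. The two versions conflict at 50.0 kg by 125 mg per dose, and boundary values at 25.0 kg, 37.5 kg, 1 m² and 1.5 m² have two rows.

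The gap above 2 m² probably has the widest practical reach, since it covers a range of body sizes and not a single value. How many subjects it touches depends on heights and weights that the documents do not give. The subjects affected are the FMT arm in the blinded phase and placebo subjects conditioned before open-label FMT. The defect lies in the dosing instructions. It does not disturb the sample size or the planned comparison.

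**What to change.** The sponsor should reconcile footnote 1 of section 5.1 with the tables of section 5.2.1 into one rule, and cite that rule in both places. The bands should not overlap, should state which side each endpoint belongs to, and should cover every weight and BSA that the eligibility criteria allow. A simple check before release is to run weights and BSA values across the eligible range and confirm that each returns exactly one row. The sponsor's clinical team and pharmacy must decide which values apply at 50.0 kg, at the shared endpoints and above 2 m²; no dose is proposed here.

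The cost is a wording amendment to two sections, and to any dispensing instructions that repeat them. Sample size and analysis are unchanged.

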5.2. Study treatment and procedures

5.2.1. Screening and Enrollment

Patients with active UC that are part of the Boston Children's Hospital Gastroenterology and Nutrition clinic as well as referrals from outside of BCH will be pre-screened for study participation. Potential subjects who agree to participate in the study will have a medical exam with labs to assess eligibility. Participants will also undergo a baseline serologic assessment of HIV, HBV and HCV status within 2 weeks prior to the first FMT dose. Females who have achieved menses will undergo urine hCG testing. These four lab tests are considered for research purposes only.

It is expected that study participants will receive ongoing clinical care at BCH for the duration of the study. Study participants, who self-refer or are referred by a GI provider not at BCH, will have their primary GI provider notified of their participation in the FMT study and follow up clinical care at BCH during the course of the study at planned intervals. The study PI will provide the primary GI provider with contact information to relay any questions and concerns during the study period. At the completion of the subject's involvement in the study, the PI will provide a final written and/or verbal report to the primary GI provider for continuity of care.

Presence of active mucosal inflammatory bowel disease (active colitis) is an eligibility requirement for this study. Subjects with evidence of inflammation in a prior staging colonoscopy completed no more than 105 days will not be required to repeat a standard staging colonoscopy solely for the purposes of research. Subjects who have no evidence of active disease by endoscopic scoring of disease at the time of staging colonoscopy will not be randomized and will be excluded from the study.

An initial subset of 10 subjects will be limited to patients with mild to moderate Ulcerative colitis (i.e., PUCAI < 65) and to individuals ≥ 12 years of age.

Upon confirmation of eligibility and completion of randomization, subjects will receive an induction antibiotic regimen (or corresponding placebo if in placebo arm) for one week to decrease levels of indigenous microflora (Study Day -8 until Day -1).

The antibiotic regimen will include:

1) A double antibiotic capsule containing vancomycin 125 mg and polymixin 62.5 mg to be administered orally (PO) according to the following body surface area (BSA) parameters:

BSA* (m ²)	Capsule	Frequency				
< 0.5	1	3 times a day				

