5.2.3. Open-label FMT or Follow-up

After completing 8 weeks of blinded study treatment, study subjects will be given the option to receive open-label maintenance FMT weekly for the remainder of the study if they initially received placebo and did not improve OR if they received FMT, improved, and wish to continue treatment. Subjects will be considered to have improved if their PUCAI score shows improvement of at least 10 points compared to baseline or a score of 10 points or less.

After a subject receives the last dose of blinded study treatment at week 8, the subject's treatment assignment will be unblinded to determine the appropriate course of action. Those subjects, who 1) are found to have improved after receiving 8 weeks of placebo or 2) are found not to have improved after receiving 8 weeks of FMT, will not be eligible to receive open-label FMT. Those subjects will be considered in follow up and will have disease status assessments conducted weekly for the 1st month and then monthly for the following month or 5 months. Subjects will also collect a stool sample and have medical examinations done at 3 and 6 months after their last dose of FMT.

Study subjects who are eligible and interested in continuing on to open-label FMT can be enrolled within 14 days (\pm 7 days) following blinded treatment completion. For the open label phase, subjects who received active treatment (FMT) will proceed directly to open label treatment weekly capsules. However, subjects randomized to placebo (aka no antibiotics, no FMT) will undergo a 7-day antibiotic conditioning and a 2-day rest period prior to commencing open-label FMT treatment that will begin with a retention enema. Thereafter, all subjects will return weekly for observed FMT administration as previously described, AE assessment and survey and stool collection. Routine laboratory assessments and medical exams will be conducted monthly. At all times during this study, standard of care progression of medical/surgical therapy will be offered if clinical course dictates it is necessary for both FMT and placebo arms of the study.

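### The 30-day waiver of the Day -8 pregnancy test conflicts with the 2-week limit on the same schedule row, so a test up to 38 days old can be the last before the first dose.

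*Combined protocol and SAP*

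**What the plan says.** The hCG row of the Schedule of Events (section 5.1) carries two timing rules.

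- Footnote 3 is attached to the row label and covers the three viral tests and hCG together. They are "required to be obtained no earlier than 2 weeks prior to the 1st FMT dose".
- Footnote 8 is attached to the Day -8 hCG cells of both the blinded and the open-label phase: "A urine pregnancy test should only be obtained on day -8 if one has not been done in the past 30 days".

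In the blinded phase the row is marked at screening (Day -90 to Day -9), Day -8, week 4 and week 8. It is blank at Day -1 and Day 0.

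The body text adds no hCG window. Section 5.2.1 gives the 2-week limit for the viral tests ("Participants will also undergo a baseline serologic assessment of HIV, HBV and HCV status within 2 weeks prior to the first FMT dose") and then treats pregnancy testing in its own sentence: "Females who have achieved menses will undergo urine hCG testing". Inclusion criterion 4 (section 3.2.1) requires only this: "Have a negative urine hCG test if female of childbearing potential".

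**The concern.** Footnote 8 governs the decision on Day -8, and its answer is not to test if any result from the previous 30 days exists. Footnote 3 counts 2 weeks back from the first dose, eight days later. A result can therefore be recent enough to waive the Day -8 test and too old to satisfy footnote 3. With nothing scheduled on Day -1 or Day 0, no later step catches this before dosing.

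At stake is the pregnancy check before a week of three antibiotics and then FMT in females who have reached menses. A site that follows footnote 8 as written can skip the only scheduled test between screening and Day 0, and so depart from footnote 3. No statistical result depends on this: the eligibility criteria state no hCG window, so the primary analysis set does not change.

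**Working it through.** The plan gives no figure to reproduce. The check is a day count from four inputs, all in section 5.1:

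- screening window: Day -90 to Day -9;
- antibiotics start: Day -8;
- first FMT or placebo dose: Day 0 (Week 1, Day 1);
- the limits: 30 days before Day -8 (footnote 8) and 14 days before the first dose (footnote 3).

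Footnote 3 refers to the first FMT dose. I read this as the first blinded FMT or placebo dose, since the tests are screening tests and staff are blinded.

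**Blinded phase.** Let the screening test fall on Day -t, with t from 9 to 90.

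1. Footnote 8 waives the Day -8 test if t - 8 ≤ 30, that is t ≤ 38. The waiving days are Day -38 to Day -9: 38 - 9 + 1 = 30 days.
2. Footnote 3 is met if t ≤ 14. Days that waive and comply are Day -14 to Day -9: 14 - 9 + 1 = 6 days.
3. Days that waive and breach are Day -38 to Day -15: 38 - 15 + 1 = 24 days.
4. Worst case, t = 38: the test is 38 - 8 = 30 days old when antibiotics start and 38 days old at Day 0.

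| Screening test on | Day -8 test under footnote 8 | Age of last test at Day 0 | Footnote 3 (≤ 14 days) |
|---|---|---|---|
| Day -39 or earlier | done | 8 days | met |
| Day -38 to Day -15 | waived | 15 to 38 days | breached |
| Day -14 to Day -9 | waived | 9 to 14 days | met |

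The ordering is perverse: the oldest screening tests lead to an 8-day-old result at dosing, while more recent ones lead to a result of 15 to 38 days.

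**Do the footnotes fit together?** A screening test that meets footnote 3 is at most 14 - 8 = 6 days old on Day -8. For such a subject the 30-day condition can never call for a test. Footnote 8 calls for one only when the screening test predates footnote 3's window, and then only if it is also more than 30 days old.

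**Open label.** Footnote 8 also marks open-label Day -8. There, placebo subjects "will undergo a 7-day antibiotic conditioning and a 2-day rest period prior to commencing open-label FMT treatment", and that dose is literally their first FMT. Section 5.2.3 allows enrollment within 14 (± 7) days of completing blinded treatment, so at most 21 days. Assume the week 8 hCG is done on the day of the last blinded dose.

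- If enrollment means open-label Day -8, that test is up to 21 days old there (waived) and up to 21 + 8 = 29 days old at open-label Day 0.
- If it means open-label Day 0, the test is up to 21 - 8 = 13 days old at Day -8 (waived) and up to 21 days old at Day 0.

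This shows that the open-label rule needs stating. It does not by itself show an error there.

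**The case against.** The best defense is that footnote 3 prevails. It is worded as a requirement and attached to the whole row, whereas footnote 8 uses softer wording and only limits repeat testing. The viral tests have the same 2-week window and are marked only at screening, so every subject already needs research blood tests on Day -14 to Day -9. Section 5.2.1 also treats hCG and the viral tests as one set of research tests. On this reading hCG is collected at that same visit, and footnote 8 merely spares a duplicate on Day -8. The study has a single center and weekly team meetings, so one agreed interpretation is feasible.

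Part of this stands. Both rules can be obeyed together, and shared timing with the viral tests makes a skipped test less likely in practice. The 24 of 30 days is a count of calendar days, not a probability, and the 38-day age arises only if footnote 3 is overlooked. The silence of section 5.2.1 and criterion 4 leaves the question open without supporting either rule.

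The defense does not remove the conflict. No rule of precedence is stated, and nothing ties the urine test to the blood draw; an earlier screening urine test fills the screening cell. If footnote 3 governed as the defense supposes, the 30-day condition would be idle in the blinded phase, as shown above. It has work to do only if older screening tests are accepted, and accepting them opens the gap.

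**Conclusion.** The concern holds. In the blinded phase, footnote 8 followed as written permits what footnote 3 forbids: a last pregnancy test 15 to 38 days old at the first dose, against a limit of 14, for screening tests on 24 of the 30 waiving days. This rests on counting 30 days inclusively from Day -8 and on applying footnote 3 to the first blinded FMT or placebo dose.

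The consequence is limited to participant safety and protocol compliance. Endpoints, power, randomization and the analysis set are untouched, and the documents give no basis for estimating how many subjects would be affected. It should be corrected because it concerns a safety check before dosing and the remedy is simple.

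**What to change.** For the blinded phase, reword footnote 8 along these lines: *Obtain a urine hCG on Day -8 unless a negative test was obtained on or after Day -14 (within 2 weeks before the first FMT/placebo dose).* This restricts the waiver to the 6 days that meet both rules. A simpler alternative is to make the Day -8 test mandatory, which gives a result 8 days old at the first dose.

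Add a separate sentence stating which window applies at open-label Day -8, where subjects crossing over from placebo start antibiotics before their first actual FMT. It need not be the same window as in the blinded phase.

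The cost is a change of footnote wording and at most one additional urine test for some subjects.
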